598 are completed and eligibility determined. This visit may occur as an in-person office visit or via
599 telecommunication. For visits occurring remotely, these relevant devices will be shipped to the
600 participant.

601 The purpose of the run-in phase is to obtain about 14 days of baseline data while the participant
602 is following their usual care with their personal t:slim X2 study pump and Dexcom G6 CGM. The
603 study team may elect to allow the participant to repeat the run-in phase as needed.

604 At Visit 2, participants will be trained on the CGM and insulin pump, if relevant, as described in
605 section 5.1 and 4.2. Participants will also be trained on blood glucose meter if relevant and the
606 ketone meter as described in section 5.5 and 4.6.

607 A pregnancy test will be repeated as needed if more than 30 days has elapsed since the
608 prior pregnancy test.

609 Study clinicians may optimize insulin pump settings if needed during this visit. Participants will
610 be allowed to make insulin dosing decisions per their usual care but will be asked to avoid
611 changing insulin pump settings during the two-week run-in.

612 **6.2 Randomization Visit (Visit 3)**

613 **6.2.1 Randomization Criteria**

614 After the completion of at least 2 weeks of run-in data, participants will have a randomization
615 visit. This visit can occur between 14-28 days from Visit 2. This visit can be conducted either in-
616 person office visit or as a remote visit.

617 Screening failures and study dropout participants may be replaced.

618 This visit may be performed as an office visit, or via telecommunication.

619 **6.2.2 Participants**

620 Participants will be randomized 1:1 to either:

621 • Group 1: Use of AID and ATM / WST for 6 weeks

CLINICAL PROTOCOL

622 • Group 2: Use of AID, ATM / WST, and BAM for 6 weeks

623 The randomization scheme will be completed prior to the first study participant and will be done
624 by a study team member who is not involved with enrollment.

625 **6.3 Optimization of Insulin Pump Settings**

626 Insulin pump optimization will occur during the study as described in Section 4.2.1.

627 **6.4 Check-In Visits (Visit 4-8)**

628 These visits will occur either as in-person office visits or remote visits. These visits will occur
629 weekly (+/- 3 day). Prior to each phone visit, participants will be asked to download any relevant

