630 devices if applicable (i.e. not using a shared web-based app for data such as the t:connect mobile
631 app or G6 mobile app). During these visits, the study team will:

632 • Answer any questions and inquire about any device complaints.

633 • Inquire about new medications, updates to medical conditions, adverse events, and
634 whether the adverse event was related to study device use.

635 • Inquire about ketone readings (a ketone meter download will not be required)

636 • Review the downloaded/uploaded data to assess completeness.

637 **6.5 Participant Study Compliance**

638 The study team may contact the study participant as needed to ensure study compliance.

639 Group 1 will be asked to have a minimum of weekly interaction to review and implement weekly
640 parameter settings.

641 Group 2 will be asked to have a minimum of weekly interaction to review and implement weekly
642 parameter settings. Participants engaging in the BAM module will be asked to have daily contact
643 with that module.

644 The study team will determine if non-compliance should result in additional study weeks or
645 discontinuation from the study.

646 **6.6 Study System Issues**

647 The study team will be available to troubleshoot with the investigational WIT, BAM, and ATM /
648 WST.

649 The AID system will used per approved use without modification.

CLINICAL PROTOCOL

650 **6.7 Repeating Visits & Unscheduled Visits**

651 Participants may have unscheduled visits during the study period if required for additional device
652 training or other unanticipated needs per the study investigator discretion.

653 **6.8 Final Visit (Visit 9)**

654 The following procedures will be performed in both groups at the final study visit:

- 655 • Adverse events, adverse device effects, and device issues
- 656 • All devices will be downloaded (i.e. insulin pump, CGM, glucometer, ketone meter)
- 657 • Study team or participant may download the study equipment
- 658 • Questionnaires will be completed electronically when possible
- 659 • Blood will be drawn for HbA1c (which can be done on-site or locally)
- 660 • Pregnancy test (if applicable)
- 661 • Equipment may be returned in person or via Federal Express

662 Study participants will be instructed on how to transition back to the home insulin regimen.
663 Subjects will be informed that there may be a risk of severe hypoglycemia and/or severe

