1013 collaborators involved in the study after the appropriate research agreement has been executed.

CLINICAL PROTOCOL

1014 Chapter 11: Statistical Consideration

1015 The intent of this pilot-feasibility study is to introduce and initially test elements of two modules
1016 to be included in a future Adaptive Biobehavioral Control (ABC) system: (1) A Behavioral
1017 Adaptation Module (BAM) and (2) An Auto Titration Module (ATM) and a Web Simulation Model
1018 (WST). BAM and ATM / WST will be provided to users of the t:slim X2 with Control-IQ closed-loop
1019 system. The only purpose of this trial is safety testing and receiving feedback from the
1020 participants regarding system functionality and user interface.

1021 11.1 Design and Randomization

1022 The study will recruit current users of the Control-IQ system. Following a 2-week baseline using
1023 Control-IQ only, the participants will be randomized 1:1 to Control-IQ + ATM / WST vs Control IQ
1024 + ATM / WST + BAM and will be followed for 6 weeks. The randomization list will use a sequence
1025 of computer-generated pseudorandom Bernoulli trials. The 6 weeks of active trial will be used
1026 for assessment of the safety and usability of ATM / WST and BAM. The baseline data and the last
1027 2 weeks of the active trial will be used for secondary comparisons of CGM-based metrics of
1028 glycemic control.

1030 11.2 Sample Size

1031 We intend to recruit up to 45 users of Control-IQ, with the objective to randomize N=30 subjects.
1032 The number of participants is a convenience sample not based on statistical principles. This
1033 sample will provide ~180 weeks of data for the assessment of the safety and utility of the ATM
1034 and up to 90 weeks for assessment of the safety and utility of the BAM.

1035 11.3 Outcome Measures

1036 11.3.1 Primary Efficacy Endpoint

1037 Safety assessment of ATM / WST and BAM.

1038 11.3.2 Secondary Outcome

1039 CGM-based metrics and user experience (UX) questionnaires, including:

CLINICAL PROTOCOL

1040 • Percentage of readings in the target ranges of 70-180 and 70-140 mg/dl;
1041 • Mean glucose;
1042 • Glucose variability measured by standard deviation and coefficient of variation;
1043 • Percentage of readings <70, 60, and 54 mg/dl;
1044 • Low blood glucose index (LBGI)¹⁰
1045 • Percentage of readings >180, 250, and 300 mg/dl;
1046 • High blood glucose index (HBGI)¹⁰
1047 • ABC Pilot Pre and Post Study Questionnaire
1048 • INSPIRE

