1049 **11.4 Safety Analyses**

1050 All randomized participants will be included in these analyses and the circumstances of all
1051 reportable cases of the following will be summarized and tabulated by treatment group:

1052 • Severe hypoglycemia;
1053 • Diabetic ketoacidosis (DKA);
1054 • Ketone events defined as a calendar day with ketone level >1.0 mmol/L;
1055 • Serious adverse events (SAE) with a possible or greater relationship to a study device
1056 (including anticipated and unanticipated adverse device effects);
1057 • Other serious adverse events not related to a study device, and
1058 • Adverse device effects (ADE) that do not meet criteria for SAE.

1059 Criteria for Success have been discussed with FDA during the submission of our previous pilot
1060 study (IDE G170255, “A Pilot Test of t:slim X2 with Control-IQ Technology”), which was used to
1061 introduce Control-IQ and enable a subsequent pivotal trial. These criteria included system safety
1062 checks and CGM-based performance criteria consistent with the recommendations of the
1063 International Consensus on Time-in-Range. Because these criteria are well established, we will
1064 keep them to gauge the success of the pilot evaluation of the new modules ATM / WST and BAM:

1065 • No critical ATM / WST or BAM errors;
1066 • No SAE or ADE related to the use of ATM / WST or BAM;
1067 • Percent time in the range 70-180 mg/dL: mean 71% \pm 11;
1068 • Percent time <70 mg/dL: median <5%.
1069 • Percent time >250 mg/dL: median <10%.

CLINICAL PROTOCOL

1070 **11.5 Baseline Descriptive Statistics**

1071 Baseline demographic and clinical characteristics of the cohort of all randomized participants will
1072 be summarized in a table using summary statistics appropriate to the distribution of each
1073 variable. Descriptive statistics will be displayed overall and by treatment group, and will include:

- 1074 • Demographics (e.g. age, duration of diabetes, and other);
- 1075 • Baseline HbA1c, and
- 1076 • CGM-based metrics from the 2-week baseline use of Control-IQ:
 - 1077 ○ Percentage of readings in the target ranges of 70-180 and 70-140 mg/dl;
 - 1078 ○ Mean glucose;
 - 1079 ○ Glucose variability measured by standard deviation and coefficient of variation;
 - 1080 ○ Percentage of readings <70, 60, and 54 mg/dl;
 - 1081 ○ Low blood glucose index (LBGI);¹⁰
 - 1082 ○ Percentage of readings >180, 250, and 300 mg/dl;
 - 1083 ○ High blood glucose index (HBGI).¹⁰

1084 **11.6 Device Issues**

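### Does Bernoulli allocation undermine the stated ceiling of 90 weeks of BAM exposure?

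*Combined protocol and SAP*

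**What the plan says.** Section 11.1 (Design and Randomization) randomizes participants 1:1 after a two-week baseline, follows them for six weeks, and builds the list as a sequence "of computer-generated pseudorandom Bernoulli trials". Section 6.2.2 adds: "The randomization scheme will be completed prior to the first study participant and will be done" by a team member who takes no part in enrollment. Neither section mentions blocks, strata or a cap on group size.

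Section 11.2 (Sample Size) aims to randomize 30 and says: "The number of participants is a convenience sample not based on statistical principles". It then describes what the sample supplies: "sample will provide ~180 weeks of data for the assessment of the safety and utility of the ATM" "and up to 90 weeks for assessment of the safety and utility of the BAM".

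Three other provisions affect exposure.
- Section 6.2.1: "Screening failures and study dropout participants may be replaced".
- Section 6.5: "The study team will determine if non-compliance should result in additional study weeks or" discontinuation.
- Sections 2.4 and 4.1 set a goal of about 30 completers, with up to 45 people consenting.

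Among the success criteria in section 11.4 is "No SAE or ADE related to the use of ATM / WST or BAM".

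**The concern.** The words *up to* state a maximum, and the allocation method a few lines earlier provides none. A ratio of 1:1 under Bernoulli trials fixes the probability for each participant, not the count in each group, so Group 2 could end with 12 people or with 18.

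This could matter because only Group 2 uses BAM, safety is the primary endpoint, and one success criterion is an absence of BAM-related serious events and device effects. How reassuring a zero count is depends on how many people were exposed and for how long. Section 11.2 gives no power or precision argument, so the two exposure totals are the only description of what the sample can show. If the BAM total were wrong in a way that mattered, the reader would misjudge the strength of the BAM safety evidence.

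**Working it through.** **Inputs.** N = 30 randomized (11.2); 1:1 by Bernoulli trials (11.1), read as p = 0.5; six weeks per participant (6.2.2, 11.1); all participants use ATM and only Group 2 uses BAM. The documents give no dropout rate, so the rates in step 4 are assumptions.

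**1. The plan's own figures.** ATM: 30 × 6 = 180 weeks. BAM: 15 × 6 = 90 weeks. Both reproduce. The ATM total does not depend on the split; the BAM total presumes 15:15.

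**2. BAM exposure under the stated method.** Let X be the size of Group 2, X ~ Binomial(30, 0.5), with exposure 6X weeks and complete follow-up.
- Mean: 6 × 30 × 0.5 = 90 weeks. SD: 6 × √(30 × 0.25) = 16.4 weeks.
- P(X = 15) = 155,117,520 / 1,073,741,824 = 14.4%.
- P(X ≥ 16) = (1 − 0.1445)/2 = 42.8%. The chance of falling below 90 weeks is the same.
- P(10 ≤ X ≤ 20) = 95.7%, that is, 60 to 120 weeks.
- P(X ≤ 12) = P(X ≥ 18) = 18.1%, that is, 72 weeks or fewer, or 108 or more.

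So 90 is the centre of the distribution and not its upper end.

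**3. What the variation costs.** With no events among n people, the one-sided 95% upper bound on per-person risk is 1 − 0.05^(1/n).

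| BAM group size | Weeks | Upper bound |
|---|---|---|
| 10 | 60 | 25.9% |
| 12 | 72 | 22.1% |
| 15 | 90 | 18.1% |
| 18 | 108 | 15.3% |
| 20 | 120 | 13.9% |

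Averaged over Binomial(30, 0.5), the bound is 18.6%, against 18.1% at a fixed 15. For the group comparison, interval width relative to 15:15 is √[(1/n₁ + 1/n₂)/(2/15)]: 1.02 at 12:18, 1.06 at 10:20, and 1.018 on average.

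**4. Dropout and replacement.** If dropouts are not replaced and contribute no weeks, expected BAM exposure is 90(1 − d): 85.5, 81 and 76.5 weeks for d = 5%, 10% and 15%. The chance of exceeding 90 falls to 32.3%, 23.1% and 15.5%. If each dropout contributes three weeks, the expectation is 15 × [6(1 − d) + 3d]: 87.75, 85.5 and 83.25. If dropouts are replaced until 30 complete, and dropout is unrelated to group, completers alone give an expected 90, and partial weeks add to it. Shortfalls are consistent with *up to*; an excess is not.

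**5. The obvious alternative.** Permuted blocks of 4 and 6, chosen with equal probability and cut at 30, give 15:15 in 77.3% of lists and 14:16 or 16:14 otherwise, so 84 to 96 weeks with full follow-up. The average zero-event bound returns to 18.1%. In the worst case, where all past allocations are known and the smaller group is always guessed, correct guesses rise from 15.0 of 30 under Bernoulli trials to 20.6 of 30. Even this list does not make 90 a strict ceiling.

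**The case for a change.** The best case for a change is this. Safety testing and participant feedback are the declared purpose, BAM is new, and its safety evidence comes from one group only. The single sentence that sizes that evidence states a ceiling which more than two lists in five would break. Correcting one phrase costs nothing, and restricted randomization would remove the chance, about 5%, of a BAM group of ten or fewer.

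The factual core of this stands: 90 is not a maximum under section 11.1. The rest carries less weight. *Up to* never promised a minimum, so a small group or some dropout does not contradict the plan. A reader judging a zero count will use the observed group size and exposure; section 11.4 includes all randomized participants and tabulates events by treatment group. The zero-event bound used above is a yardstick brought in for this check; the plan does not call for one. The risk is also symmetric, since Group 2 is as likely to be larger than 15 as smaller.

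Blocking is a legitimate preference with a real price here. There is one site, only Group 2 receives BAM training (section 5.3), and the staff running weekly visits can learn who was assigned what. Unrestricted allocation keeps the next assignment unpredictable even to someone who knows every earlier one.

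**Conclusion.** No change to the plan is needed. The phrase in section 11.2 is loose: 90 weeks is the expected BAM exposure, not its upper limit, given N = 30, p = 0.5 inferred from 1:1, six weeks each and complete follow-up. It is exceeded with probability of about 43%, and the central 95% range is 60 to 120 weeks. Complete follow-up is not the only route to that expectation, because replacing dropouts or adding study weeks can restore or raise it.

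The slip is clerical in effect. The companion ATM figure is marked approximate, the sample size is openly one of convenience, and no test, model or success criterion takes 90 as an input. Rewording the sentence would alter no result. The allocation method is a valid form of 1:1 randomization. Its average cost against a fixed 15:15 split is about half a percentage point on an unplanned bound and 1.8% on interval width, a reasonable exchange for unpredictability at a single site. The report need only state the exposure that was actually obtained.

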303 This is a safety and feasibility study with a randomized two-arm parallel group trial in which both
304 groups will use the AID (Control-IQ) plus ATM and WST. The difference between the two groups
305 will be the behavioral module. One group will be randomized to add BAM and one group will not
306 use BAM. This is illustrated in Figure 2:

CLINICAL PROTOCOL

307

308 **Figure 3: Study Diagram**

309 **2.3 Purpose/Objectives of Clinical Study**

310 This pilot study is intended to test a Web-based Information Tool (WIT) software providing
311 additional information regarding glucose variability, estimated A1c, risks for hypo- and
312 hyperglycemia, and potential changes of insulin pump parameters, to users of the Control-IQ
313 system.

314 **2.4 Study Participants**

315 Enrollment in the study will proceed with the goal of completing approximately 30 subjects.
316 Study duration is between 8-10 weeks.

317 Up to 45 participants may sign the consent form.

318 **2.5 Clinical Sites**

319 The study will be performed at the University of Virginia.

320 **2.6 Primary Specific Aim**

321 The primary outcome will be a safety assessment using all 6 weeks of treatment data in terms of
322 incidence of DKA or severe hypoglycemia.

323 **2.7 Secondary Specific Aim**

324 The secondary outcome of interest will be primarily CGM-based metrics using the last two weeks
325 of the treatment data and the two-week baseline to compare:

326 • ATM / WST vs. Baseline
327 • ATM / WST + BAM vs. Baseline
328 • Group 1 vs. Group 2: ATM / WST vs. ATM / WST + BAM.

CLINICAL PROTOCOL

329 **Chapter 3: Study Devices**

330 **3.1 Insulin Pump**

331 Participants will use their personal FDA-approved Tandem t:slim X2 with Control-IQ Technology
332 which will be used without modifications.

333 **3.2 Continuous Glucose Monitor**

334 Participants will be provided a study provided CGM that includes Dexcom G6 transmitter and
335 sensors while using the Tandem t:slim X2 insulin pumps. The CGM sensor is viable for 10 days.
336 All participants will be provided a Dexcom G6 system by the study team as needed. This system
337 will be used without modifications. The CGM device will be calibrated, if needed, using the
338 glucometer in accordance with the manufacturer's labeling. The participant may elect to
339 continue use of their personal CGM during the study. The study will provide CGM supplies, as

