1085 The following tabulations and analyses will be performed by treatment group to assess device
1086 issues:

- 1087 • Device malfunctions requiring study team contact and other reported device issues
- 1088 • Sensor performance metrics (difference, absolute relative difference, and International
1089 Organization for Standardization criteria) – if applicable, by sensor version.
- 1090 • % time CGM data available - overall and by month
- 1091 • % time in different operational modes per week - overall and by month

1092 **11.7 Analysis of Secondary CGM-based Outcomes**

1093 The study design includes repeated measures (baseline vs last 2 weeks of study) on all secondary
1094 CGM and UX outcomes (Figure 1); thus, we will use a linear mixed-effect model that corresponds
1095 well to this structure^{5,6} (e.g. Linear Mixed Models in SPSS.⁷), with “Subject” as a random factor
1096 and “Group” as a fixed factor. The models will adjust for age and HbA1c as fixed effects. We
1097 should note that similar results may be generated by repeated measures ANOVA, but mixed
1098 models handle missing data better (e.g. ANOVA only uses listwise deletion, which could reduce
1099 power and introduce bias towards study completers).^{8,9}

1100 The general principles that will be followed during analysis are:

- 1101 • The analysis will follow an Intention-to-treat (ITT) approach;

CLINICAL PROTOCOL

1102 • All randomized participants will be included in the primary safety analysis and in the
1103 secondary analyses of CGM metrics.

1104 • All covariates obtained on a continuous scale will be entered into the models as
1105 continuous variables, unless it is determined that a variable does not have a linear
1106 relationship with the outcome. In such a case, categorization and/or transformation will
1107 be explored. All p-values will be two-sided.

1108 • Standard residual diagnostics will be performed for all analyses. If values are highly
1109 skewed, then an alternate transformation or nonparametric methods will be used.
1110 Previous experience suggests that no transformation or nonparametric analyses will be
1111 necessary for TIR 70-180 mg/dL, TIR above 180 mg/dL, mean glucose, or HbA_{1c}. Other
1112 outcomes, such as TIR below 70 mg/dL are typically skewed.

CLINICAL PROTOCOL

1113 **Chapter 12: Data Collection and Monitoring**

1114 **12.1 Case Report Forms and Device Data**

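### The three CGM success levels in 11.4 are not tied to the Control-IQ run-in, so they mainly reflect Control-IQ and not the new modules; 11.7 should name period and group-by-period

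*Combined protocol and SAP*

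**What the plan says.** Section 11.4 (Safety Analyses) takes its success criteria from the earlier pilot that introduced Control-IQ and says the plan will "keep them to gauge the success of the pilot evaluation of the new modules ATM / WST and BAM". There are five. Two are specific to the modules: no critical module errors, and no SAE or ADE related to module use. The other three are CGM levels: "Percent time in the range 70-180 mg/dL: mean 71"% ± 11; "Percent time <70 mg/dL: median <5"%; and a median below 10% for time above 250 mg/dL. None refers to the run-in.

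Under 11.1, participants spend a 2-week baseline on Control-IQ only. They are then randomized to ATM/WST or ATM/WST plus BAM, so both groups receive ATM/WST.

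Two time windows are defined elsewhere. Section 2.6 states: "The primary outcome will be a safety assessment using all 6 weeks of treatment data in terms of" DKA or severe hypoglycemia. Section 2.7 states: "The secondary outcome of interest will be primarily CGM-based metrics using the last two weeks" of treatment and the baseline, and lists each group against baseline and Group 1 against Group 2. Section 11.1 agrees ("2 weeks of the active trial will be used for secondary comparisons of CGM-based metrics of" glycemic control). Section 11.5 tabulates the run-in CGM metrics overall and by group.

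Section 11.7 opens: "The study design includes repeated measures (baseline vs last 2 weeks of study) on all secondary" CGM and questionnaire outcomes. It then names the model terms: Subject as random, Group "as a fixed factor. The models will adjust for age and HbA1c as fixed effects".

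**The concern.** A level set when Control-IQ was the new device is reused to judge something added to Control-IQ. Whether the cohort meets it depends first on how well these people were already doing on Control-IQ. A cohort that starts comfortably inside the levels can lose ground and still pass. A cohort that starts outside them can be unchanged and fail.

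Because both groups receive ATM/WST, the randomized comparison says nothing about ATM/WST itself; it isolates only the addition of BAM. For CGM outcomes, the only contrast bearing on ATM/WST is each participant's follow-up against the run-in. The plan collects and reports that contrast but leaves it out of the success judgement. In addition, the terms listed for the model meant to deliver it do not include the one that would estimate it.

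**Working it through.** **The plan's own figures.** The only derived numbers are the exposures in 11.2: 30 × 6 = 180 weeks for ATM and 15 × 6 = 90 for BAM. Both reproduce. The three CGM levels have no derivation in the documents, and the documents give no run-in values, SDs or correlations. Everything below that needs such values is therefore an assumption, and shows what could happen, not what is likely.

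**1. Can a level be met after worsening?** Take time below 70 mg/dL as lognormal across participants, log-SD 0.6, 0.8 or 1.0, N=30. Let the true median double from 2% in the run-in to 4% at follow-up.

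- By simulation, the probability that the sample median is below 5% when the true median is 4% is 0.95, 0.89 and 0.84.
- The expected number of participants at or above 5% is 30 × [1 − Φ(ln(5/m)/log-SD)]. At m = 2% this is 1.9, 3.8 and 5.4; at m = 4% it is about 10.6, 11.7 and 12.4.

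So the level would usually be met while the number of participants at or above 5% rose from about 2–5 to about 11–12 of 30.

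**2. Can a level be missed with no change?** If the true median is 5% in both periods, the sample median falls on the failing side about half the time, with no module effect at all.

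**3. What do the terms named in 11.7 estimate?** Each participant contributes a baseline and a follow-up value. With Group as the only design effect, the Group coefficient averages the two periods. If groups are alike at baseline and BAM adds δ at follow-up, the coefficient is (0 + δ)/2. Simulation check (400 trials, 15 per group, assumed SD 11 and correlation 0.65, a change of −4 points in both groups and an extra +6 in Group 2; age and HbA1c left out):

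| Model | Group or interaction | Change from baseline |
|---|---|---|
| Group only | 3.06 (expected 6/2 = 3) | no term |
| Group, period, group-by-period | 6.16 | −4.14 |

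The first model has no term for either of the two contrasts with baseline in 2.7.

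**4. How precise would the paired change be?** SE = √(2 × SD² × (1 − r)/n), SD 11, r 0.8 to 0.5, t quantiles with n − 1 degrees of freedom.

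- n=30: SE 1.27 to 2.01, times 2.045, gives ±2.6 to ±4.1 points.
- n=15: SE 1.80 to 2.84, times 2.145, gives ±3.9 to ±6.1 points.

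Section 11.1 randomizes by Bernoulli trials, so 15 per group is not guaranteed. With N=30 an exact 15/15 split has probability 0.14, and the 95% range of one group's size is about 10 to 20.

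**The case against.** The best defence is that the link to baseline largely exists. Run-in metrics are tabulated (11.5) and changes from baseline are planned (2.7, 11.1, 11.7). Two success criteria are specific to the modules, and causality is assessed event by event (9.3). Chapter 11 describes the trial's purpose as safety testing and user feedback, for which absolute levels can serve as acceptability benchmarks. All of this stands. It limits the gap to how success is read, not what is collected.

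On the model, the repeated-measures wording and the contrasts in 2.7 imply a period factor, so the half-size coefficient describes a literal reading that the authors probably do not intend. That also stands; the request is to name the terms.

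Three stronger readings are tempting, and the documents do not support them:

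- *That 71% is a floor, so a cohort at 65% fails.* Section 11.4 writes a less-than sign for the two medians but no inequality for the mean. Mean ± SD is the most natural reading, and it gives no pass rule. The ±11 may have been defined in the earlier submission, which is not available here.
- *That the plan treats passing as proof that control was unharmed, or as a go/no-go rule.* It says neither.
- *That the analysis set and weeks are wholly open.* Section 11.4 includes all randomized participants in the safety analyses, and the placement under safety makes all 6 weeks the natural default. What remains is that 11.4 does not assign a window to these levels, and 10.2 lets the study team decide whether data from withdrawn participants are used.

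**Conclusion.** The concern holds in a limited form. The CGM part of the success judgement rests on levels that mainly reflect Control-IQ and can be met after worsening or missed without change. The contrast that bears on ATM/WST is planned but sits outside that judgement. The 84 to 95% figure depends on an assumed lognormal spread and an assumed doubling from 2% to 4%; the actual run-in level is unknown, so how much worsening could pass is unknown too. The halving of a BAM effect follows algebraically from the listed terms, but applies only if 11.7 is fitted literally. The meaning of ±11, the weeks, and pooled or by group are missing detail, worth settling in the same amendment. The primary outcome (DKA or severe hypoglycemia) and the two module-specific criteria are untouched. Severity is minor to moderate.

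**What to change.** In 11.4:

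- Keep the two module-specific criteria, and keep the three CGM levels as descriptive benchmarks.
- State that the CGM part of success is read from the paired change, run-in to last 2 weeks, in time 70–180, <70 and >250 mg/dL. Give 95% confidence intervals (bootstrap or nonparametric for the skewed metrics), pooled and by group, beside the run-in values. Treat it as an estimate, not a pass/fail test. Group 1 alone shows ATM/WST without BAM; the pooled change mixes in any BAM effect.
- State what ±11 means, which weeks the levels use, whether they apply pooled or by group, and how withdrawn participants are handled.

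In 11.7, name period and group-by-period as fixed effects, the interaction being the BAM contrast.

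The cost is a short amendment with IRB approval (13.2), using data already collected. Continuity with the earlier pilot is kept, because the levels remain.

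The limits should be stated with the results. The before-after change is uncontrolled. The run-in may not be a settled baseline: pump settings may be optimized at Visit 2 (6.1), and inclusion criterion 5 admits people only expected to be on Control-IQ by then. Settings may also be changed for safety during follow-up (5.2.1). Intervals by group will be wide, and group sizes may be unequal.

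### The secondary mixed model names no Period or Group×Period term, so its Group coefficient estimates only half the BAM effect and no term gives each group's change from baseline

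*Combined protocol and SAP*

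**What the plan says.** Section 2.7 sets three secondary comparisons, based on the two-week baseline and the final two weeks of treatment: "ATM / WST vs. Baseline", "ATM / WST + BAM vs. Baseline" and "Group 1 vs. Group 2: ATM / WST vs. ATM / WST + BAM". Section 11.1 repeats the time windows: the baseline data and the last "2 weeks of the active trial will be used for secondary comparisons of CGM-based metrics of" glycaemic control.

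Section 11.7 gives the model. It begins "The study design includes repeated measures (baseline vs last 2 weeks of study) on all secondary" outcomes, and continues "thus, we will use a linear mixed-effect model that corresponds" to that structure. The terms it names are Subject as a random factor "and “Group” as a fixed factor. The models will adjust for age and HbA1c as fixed effects". It adds that the authors "should note that similar results may be generated by repeated measures ANOVA, but mixed" models deal better with missing data.

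The synopsis and section 6.2.2 define Group as the randomised arm: Group 1 without BAM, Group 2 with BAM. Neither section 2.7, 11.1 nor 11.7 names a Period term or a Group×Period term, or says which coefficient answers which comparison.

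**The concern.** Both the baseline and the follow-up value enter as outcomes, and Group takes the same value on both records of a participant. A Group main effect therefore describes a difference averaged over the two periods. Baseline precedes randomisation, so half of that average contains no BAM effect.

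An analyst who fits the listed terms, or adds only a Period main effect, would report a diluted estimate of BAM versus no BAM, which is the trial's only randomised contrast. That analyst also could not report a separate change from baseline for each group, although section 2.7 asks for both. The pilot is meant to inform a later system, so a halved BAM estimate could be carried into its planning.

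**Working it through.** **The plan's own figures.** Section 11.7 gives no number to reproduce. The only computable figures nearby are in section 11.2: 30 × 6 = 180 participant-weeks for ATM and 15 × 6 = 90 for BAM. Both agree with the text and imply about 15 per group.

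**Set-up.** Let μ be the baseline mean, common to both groups in expectation because randomisation follows the baseline period. Let τ be the change in Group 1 and τ + δ the change in Group 2. The three section 2.7 comparisons are then τ, τ + δ and δ, where δ is the BAM effect. Subject is a random intercept with within-participant correlation ρ. The values of τ, δ and ρ are assumptions; the documents give none.

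**Listed terms, complete pairs.** Group is constant within a participant, so its coefficient is the difference between groups in the two-period mean:

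[μ + (τ + δ)/2] − [μ + τ/2] = δ/2.

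This does not depend on ρ, the SD or the size of δ. No parameter represents τ or τ + δ.

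**Period main effect added.** Group is still δ/2. With equal groups the single Period coefficient is [τ + (τ + δ)]/2 = τ + δ/2, applied to both groups.

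**Group×Period added.** Period = τ, Period + Group×Period = τ + δ, and Group×Period = δ.

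With assumed changes of 3 and 7 points (τ = 3, δ = 4):

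| Fixed effects | Coefficient read as BAM effect | Change, Group 1 | Change, Group 2 |
|---|---|---|---|
| Listed terms | 2 | none | none |
| + Period | 2 | 5 | 5 |
| + Period and Group×Period | 4 | 3 | 7 |
| True values | 4 | 3 | 7 |

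A second set of assumed values (τ = 2, δ = 5) gave Group = 2.5 with and without Period, at ρ = 0.3, 0.5, 0.7 and 0.9. The same held with unequal groups of 10 and 20.

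**Missing follow-up.** Let a fraction m in each group have baseline only, missing completely at random. A complete pair carries weight 2/(1 + ρ) and has an expected group difference of δ/2. A baseline-only record carries weight 1 and an expected difference of 0. Hence

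fraction of δ estimated = 0.5 · w/(w + m), with w = 2(1 − m)/(1 + ρ).

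For m = 0.1 and ρ = 0.6: w = 1.8/1.6 = 1.125, and 0.5 × 1.125/1.225 = 0.4592.

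| m | ρ = 0.6 | ρ = 0.7 | ρ = 0.8 |
|---|---|---|---|
| 0 | 0.5000 | 0.5000 | 0.5000 |
| 0.1 | 0.4592 | 0.4569 | 0.4545 |
| 0.2 | 0.4167 | 0.4124 | 0.4082 |

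Solving the generalised least squares equations directly gives the same fractions, with or without Period. With Group×Period the fraction is 1.000 throughout.

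**Simulation check.** 1,000 simulated trials, 15 per group, with age and HbA1c as covariates, SD 11 and ρ = 0.7 (both assumed), τ = 3, δ = 4, fitted by REML. Monte Carlo standard error is at most 0.12.

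| Follow-up missing | Group, listed terms | Group, + Period | Group×Period | Changes, Groups 1 and 2 |
|---|---|---|---|---|
| 0% | 2.02 | 2.02 | 3.98 | 3.03, 7.00 |
| 10% | 1.90 | 1.88 | 3.94 | 2.95, 6.89 |
| 20% | 1.46 | 1.43 | 4.11 | 2.93, 7.04 |

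**The case against.** The strongest reply is that the interaction is already implied. Section 11.7 describes a repeated-measures structure and likens the model to repeated-measures ANOVA, which for two groups and two occasions ordinarily includes Time and Group×Time. Section 2.7 asks for a change from baseline in each group, which neither deficient model can supply, so an attentive analyst would notice the gap. It stands that a time factor was probably intended. It does not settle the matter: repeated-measures ANOVA also produces a between-subject Group test that averages over both periods, and Group is the only treatment term section 11.7 names. The text must say that the interaction is the answer.

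A second reply is that a three-level factor (baseline, ATM/WST, ATM/WST + BAM) would recover the full effect. That is correct arithmetically, but the protocol defines Group as the randomised arm, so this is not what the sentence says.

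A third is proportion. This is a pilot with a convenience sample, no power claim and a safety primary outcome, and the test of Group remains valid when BAM has no effect. All of that stands and limits the consequence. It does not make a halved estimate acceptable for comparisons that the plan itself prespecifies.

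**Conclusion.** The concern holds. Followed as written, or with only a Period main effect added, the model estimates half of the BAM effect and gives no separate change from baseline for either group.

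The factor of exactly one half is an expected value. It requires Group to be coded as the randomised arm on both records, complete pairs, and the HbA1c covariate held at its screening value, which is the natural reading. It needs no assumption about SD, correlation or effect size. The smaller fractions under missing follow-up rest on the assumed correlations and on equal, completely random missingness.

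The effect is confined to the secondary outcomes analysed under section 11.7. The primary safety assessment and the success criteria in section 11.4 do not use this model.

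**What to change.** In section 11.7, state that the fixed effects include Period (baseline, last 2 weeks) and Group×Period alongside Group, age and screening HbA1c. Then assign one quantity to each section 2.7 comparison:

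- Group 1 versus Group 2: the Group×Period coefficient.
- ATM/WST versus baseline: the Period contrast within Group 1.
- ATM/WST + BAM versus baseline: the Period contrast within Group 2.

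For the between-group comparison, a model with a common baseline mean, or ANCOVA of the last-2-week value on the baseline value, is an optional and more precise alternative. ANCOVA drops participants with no follow-up value, which would need to be squared with the plan to include everyone randomised.

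The cost is two or three sentences of analysis text, with no new data or participants.
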